12.6.2.1 Main Analysis

Missing Data Strategy

The outcome data that will be missing or set to missing following an intercurrent event, will be assumed to be missing at random (MAR) and will be handled through model-based restricted maximum likelihood (REML) estimates.

Statistical Model

A mixed model analysis of variance (ANOVA) will be conducted on AUCs, and C_{max} endpoints in the natural logarithmic scale.

The model will include terms for sequence, period, product exposure as fixed effects and subject as a categorical random effect modeling the within subject correlations.

An heterogeneous Compound Symmetry matrix will be used to model the variancecovariance structure within subjects. If this model fails to converge, then the following variance-covariance matrix will be used (in this order) until one converges. Variance Components, Compound Symmetry, and finally no repeated statement.

Confidentiality Statement

Philip Morris Products S.A.	Clinical Study Protocol	Confidential
P5-PK-01-EXP	2.0, Approved	Page 82 of 98
Related to QMS-0017588		Document ID: VV-TMF-00821

The procedure will use the restricted maximum likelihood method and the Kenward-Roger method to compute the degrees of freedom.

The results of this analysis will be presented in terms of geometric least square mean ratios and 95% confidence intervals (95% CI) for the 4 respective variants of NP 1.0, Velo-NP and Zyn-NP ratios. The pairwise comparisons which will be performed are listed in Table 10.

	NP-2	NP-3	NP-4	Velo-NP	Zyn-NP
NP-1	X	X	x	X	X
NP-2		x	x	X	x
NP-3			x	x	x
NP-4				x	x

Table 10 List of pairwise comparisons

The model described above will be implemented in the SAS® language as:

```
PROC MIXED data=dataset method=reml;
    class Subject Sequence Period Product Sex;
    model Log(Parameter) = Sequence Period Product / ddfm=KR;
    repeated Product / subject=Subject type=csh;
    lsmeans Product / pdiff=LIST_OF_PAIRWISE_COMPARISONS cl;
PUN.
```

RUN;

The analysis of T_{max} will be performed by conducting a Wilcoxon signed rank test and calculating the median T_{max} for each product along with the Hodges-Lehmann estimate of the median difference between products, and the related 95% CI.

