For the purposes of background-correction of the plasma concentrations post-baseline the following formula will be applied: $cC_t = C_t - C_0 \cdot *e^{-\lambda z \cdot t}$. Where, cC_t is the corrected concentration at each time point, C_t is the observed concentration at each time point, C_0 is the pre-use baseline concentration, λ_z is the Day 2 terminal elimination rate constant, t is the actual time since start of product use, and t is the actual time since the time of the pre-use baseline sample.

In particular, the following PK parameters will be derived from background-corrected nicotine levels following 30 minutes of product use:

C_{max}	Maximum background-corrected plasma concentration. C_{max} will be reported as long as there is at least one quantifiable concentration post T_0 .
T_{max}	Time to maximum background-corrected plasma nicotine concentration $C_{\text{\scriptsize max}}.$
AUC _{0-5min}	Area under the background-corrected plasma concentration-time curve from start of product use (T_0) to 5 minutes.
AUC _{0-10min}	Area under the background-corrected concentration-time curve from T0 to 10 minutes.
AUC _{0-15min}	Area under the background-corrected concentration-time curve from T0 to 15 minutes.
AUC _{0-20min}	Area under the background-corrected concentration-time curve from T0 to 20 minutes.

Statistical Analysis Plan Number CA36095

AUC _{0-25min}	Area under the background-corrected concentration-time curve from T0 to 25 minutes.
AUC _{0-30min}	Area under the background-corrected concentration-time curve from T0 to 30 minutes.
AUC _{0-35min}	Area under the background-corrected concentration-time curve from T0 to 35 minutes.
AUC _{0-40min}	Area under the background-corrected concentration-time curve from T0 to 40 minutes.
AUC _{0-1h}	Area under the background-corrected concentration-time curve from T0 to 1 hour.
AUC _{0-3h}	Area under the background-corrected concentration-time curve from T0 to 3 hours.
AUC _{0-6h}	Area under the background-corrected plasma nicotine concentration-time curve from T_0 to 6 hours.
$AUC_{0\text{-infinity}}$	Area under the background-corrected plasma nicotine concentration-time curve extrapolated from T0 to infinity.

All AUC parameters will be calculated using linear trapezoidal with linear interpolation method.

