For calculation of λ_z from observed data (to be used for background correction), concentrations BLQ will be set to 0 for pre-administration and prior to the first measurable concentration and set to missing after the last quantifiable concentration (if applicable).

The following steps will apply for the other PK parameters:

- Concentrations BLQ will be set to ½ the LLOQ except for any BLQ values after the last quantifiable concentration which will be set to missing.
- The formula for background correction will be applied.
- After the calculation, pre-product administration values will be assigned a value of zero in the analyses. All other values obtained will be reported as is even if these values are BLQ, except for any negative values, which will be set to zero.

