6.4 Pharmacokinetic Data Summarization and Presentation

SAS software (Version 9.4, Cary, North Carolina) will be used for all data presentation and summarization including statistical analyses, summary tables, graphs, and data listings.

Plasma nicotine concentrations (observed and background-corrected), λ_z (observed only), and other PK parameters (background-corrected only) will be summarized with descriptive statistics including number of subjects (n), number and percent of subjects with missing data (Missing, n (%)), arithmetic mean (Mean), standard deviation (SD), percent CV (CV%), standard error of the mean (SEM), minimum, first quartile (Q1), median, third quartile (Q3), and maximum.

Statistical Analysis Plan Number CA36095

In addition, geometric mean (Geo. Mean), 95% geometric confidence interval (Geo. 95% CI), and geometric CV (Geo. CV%) will be presented, as applicable.

For observed plasma nicotine concentrations, the number and percent of values below LLOQ (BLQ, n(%)) and above ULOQ (ALQ, n(%)) will be presented in each summary table.

Categorical variables will be summarized by frequency statistics (number and percentage).

For endpoints relating to sampling times (e.g., T_{max}) only n, missing n (%), median, Q1, Q3, minimum and maximum will be presented.

All analyses and summaries will be performed by product and overall. Summaries will be further stratified by sex.

The analytical data will be presented in the tables/listings to the same precision as received from the analytical laboratory.

The level of precision and rounding for the summary statistics will be specified in the TFL shell document.

Where individual data points are missing because of dropouts or other reasons, the data will be summarized based on reduced denominators. Missing PK data will be treated as missing, and no data imputation will be conducted.

Mean and individual plasma nicotine concentrations will be presented graphically (linear and semi-log plots; linear plots will be presented with and without SD).

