6.5 Statistical Analysis of PK Parameters

6.5.1 Main analysis

A mixed model analysis of variance (ANOVA) will be conducted on AUC and C_{max} endpoints in the natural logarithmic scale.

The model will include terms for sequence, period, and product as fixed effects, and subject as a categorical random effect, modeling the within subject correlations.

A heterogeneous Compound Symmetry matrix will be used to model the variance covariance structure within subjects. If this model fails to converge, then the following variance-covariance matrices will be used (in this order) until one converges: variance Components, Compound Symmetry, and finally without subject's random effect.

The procedure will use the restricted maximum likelihood method and the Kenward-Roger method to compute the degrees of freedom.

The results of this analysis will be presented in terms of geometric least square mean ratios and 95% CI for the 4 respective variants of NP 1.0, Velo-NP, and Zyn-NP ratios. The pairwise comparisons which will be performed are listed in Table 6.2.

Philip Morris Products S.A.

Nicotine pouch (NP) 1.0, P5-PK-01-EXP

Statistical Analysis Plan Number CA36095

Table 6.2 List of pairwise comparisons

	NP-2	NP-3	NP-4	Velo-NP	Zyn-NP
NP-1	X	X	X	X	X
NP-2		X	x	X	X
NP-3			X	X	X
NP-4				X	X

The model described above will be implemented in the SAS® language as:

PROC MIXED data=dataset method=reml;

class Subject Sequence Period Product Sex;

model Log(Parameter) = Sequence Period Product / ddfm=KR;

repeated Product / subject=Subject type=csh;

lsmeans Product / pdiff=LIST OF PAIRWISE COMPARISONS cl;

RUN;

The analysis of T_{max} will be performed by conducting a Wilcoxon signed rank test and calculating the median T_{max} for each product along with the Hodges-Lehmann estimate of the median difference between products, and the related 95% CI.

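### Early partial AUCs that come out at exactly zero have no rule before the log transform, so they would drop out of the ratio analysis because of their own value

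*SAP*

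**What the plan says.** SAP 6.3 prescribes four steps in order.

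- Values below quantification: "Concentrations BLQ will be set to ½ the LLOQ except for any BLQ values after the last quantifiable concentration".
- Background correction: the pre-use concentration, decayed at the subject's terminal rate, is subtracted from each later concentration.
- After correction, "pre-product administration values will be assigned a value of zero in the analyses"; the remaining values are kept, "except for any negative values, which will be set to zero".
- "All AUC parameters will be calculated using linear trapezoidal with linear interpolation method".

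SAP 6.5.1 continues: "A mixed model analysis of variance (ANOVA) will be conducted on AUC and C_{max} endpoints in the natural logarithmic scale". Its code is "model Log(Parameter) = Sequence Period Product / ddfm=KR", with no offset and no instruction for an AUC of zero.

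On missing values, SAP 6.4 says "Missing PK data will be treated as missing, and no data imputation will be conducted". Protocol 12.6.2.1 says that outcomes missing or set to missing after an intercurrent event "will be assumed to be missing at random (MAR) and will be handled through model-based restricted maximum likelihood (REML) estimates". Neither text mentions a computed AUC of zero.

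AUC0-5min and AUC0-10min are listed endpoints and belong to the primary estimand, with the geometric mean ratio as summary (Protocol 12.6.2).

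**The concern.** Each step is ordinary alone; the combination causes the trouble. Flooring turns a small or negative early uptake into exactly zero, and the log scale cannot hold a zero. The profile then disappears from the product comparison because of the quantity being compared.

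REML does not repair this. The subject's other five records stay, so the model in effect treats the lost record as if it would have been an ordinary positive value. If products differ in early delivery, which is what the study sets out to describe, the loss will probably differ between them too.

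The plan's own design makes the condition plausible. Protocol 4.2 says complete wash-out would need about three days, whereas the minimum abstinence is 8 hours, so pre-use levels can be well above zero. It also places the start of the terminal phase at 8 to 10 hours, so some baselines may still be falling faster than the terminal rate used to correct them.

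At stake are the two earliest delivery measures: their ratios could rest on profiles selected by outcome, with no planned table showing how many were lost.

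**Working it through.** **The plan's own figure.** The only design figure that can be recomputed is the Cmax precision of 15% or less with 24 subjects (Protocol 12.9.5). With GCV 40% and correlation 0.7: σ = √ln(1 + 0.40²) = 0.385; SD of the within-subject log difference = 0.385 × √(2 × 0.3) = 0.298; precision = exp(1.96 × 0.298/√24) − 1 = 12.7%, or 13.4% with t on 23 df. It reproduces and is not in dispute.

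**When is AUC0-5min zero?** With the zero placed at T0, AUC0-5min = ½ × 5 × (0 + cC5) = 2.5 × cC5, where cC5 is the corrected 5-minute value. The pre-use sample is 5 minutes before T0, so 10 minutes separate it from the 5-minute sample. With the 17-hour half-life of Protocol 4.2, the decay factor is exp(−ln 2 × (10/60)/17) = 0.993. AUC0-5min is therefore zero whenever observed C(5 min) ≤ 0.993 × C0. AUC0-10min = 2.5 × cC5 + 2.5 × (cC5 + cC10) is zero only if both early values are floored.

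If the baseline were still falling at the protocol's initial half-life of 1.35 hours, its true factor would be exp(−ln 2 × (10/60)/1.35) = 0.918. The correction would then over-subtract by up to 0.993 − 0.918 = 7.5% of C0. This is an upper bound.

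**Both samples below quantification.** Both become LLOQ/2, so cC5 = (LLOQ/2) × (1 − 0.993227) = 0.003386 × LLOQ, which carries no information on uptake.

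| Assumed LLOQ (ng/mL) | AUC0-5min (ng·min/mL) | Log |
|---|---|---|
| 0.1 | 0.00085 | −7.07 |
| 0.2 | 0.00169 | −6.38 |
| 0.5 | 0.00423 | −5.46 |

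A real rise of 0.1 ng/mL gives 2.5 × 0.1 = 0.25, log −1.39. At LLOQ 0.2, one such record in place of 0.25 shifts a 24-record log mean by (−6.38 + 1.39)/24 = −0.208, lowering that product's geometric mean by about 19%.

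**How often, and how large?** The inputs below are assumptions, not figures from the documents:

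- Baseline 0.5 to 3 ng/mL, assay CV 5% to 10%, LLOQ 0.2 ng/mL.
- Rise at 5 minutes 0.1 to 1.0 ng/mL for 3.6 mg pouches and 8.4/3.6 = 2.33 times that for 8.4 mg pouches; rise at 10 minutes three times that at 5 minutes.
- True baseline half-life 4 or 17 hours, corrected with 17 hours; GCV 40%.

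The SAP rules were applied in order, zeros dropped and geometric means compared. The true low/high ratio is 3.6/8.4 = 0.429. Selected scenarios:

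| Baseline, CV, low rise, half-life | Zero AUC0-5min, low / high | Zero AUC0-10min, low / high | Ratio AUC0-5min | Ratio AUC0-10min |
|---|---|---|---|---|
| 1, 5%, 1.0, 17 h | 0% / 0% | 0% / 0% | 0.427 | 0.429 |
| 0.5, 5%, 0.1, 4 h | 3.7% / 0.2% | 0.1% / 0% | 0.390 | 0.401 |
| 2, 10%, 0.3, 17 h | 15.4% / 3.7% | 1.3% / 0.1% | 0.476 | 0.413 |
| 2, 5%, 0.1, 17 h | 22.2% / 7.4% | 3.0% / 0.2% | 0.535 | 0.423 |
| 3, 10%, 0.1, 4 h | 44.7% / 32.0% | 20.0% / 7.4% | 0.775 | 0.564 |

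Hand check of the fourth row, without between-subject spread. For the low pouch, observed C(5 min) averages 2 × 0.993 + 0.1 = 2.09. The SD of the corrected value is √((0.05 × 2.09)² + (0.05 × 1.99)²) = 0.144, so P(zero) = Φ(−0.1/0.144) = 24%. For the high pouch, Φ(−0.233/0.149) = 6%. Both agree with the simulation.

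Over all scenarios the AUC0-5min ratio ran from 0.39 to 0.78 (−9% to +81% of the truth) and the AUC0-10min ratio from 0.38 to 0.58. With a 1.0 ng/mL rise, zeros were about 5% at most and the AUC0-5min ratio 0.40 to 0.43. These are plain geometric mean ratios, not fits of the planned heterogeneous compound-symmetry model.

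**The case against.** Several points on the other side stand.

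- **Which products.** A reader might infer that the losses fall mostly on the low-nicotine pouches. The documents do not support that. Protocol 2.1.2 reports that content per pouch did not correlate directly with absorption, and the variants also differ in pH and moisture. The ordering in the table follows from assuming uptake proportional to content. Only a weaker statement is safe: probably more often for products with low early delivery.
- **Missing at random.** A reader might infer that the plan declares these zeros missing at random. It does not. That assumption is tied to intercurrent events, and Protocol 12.6.2 lists non-adherence to product use, non-adherence to abstinence, and discontinuation. A computed zero is none of these. The plan is silent, and the software default drops the record.
- **Size.** Every input to the simulation is assumed, and the range includes no effect. Zeros in AUC0-10min are much rarer than in AUC0-5min.
- **Visibility.** SAP 6.4 reports minimum, quartiles and arithmetic mean of the parameters by product, so a cluster of zeros would partly show. The supplementary analysis in SAP 6.5.3 removes some high-baseline periods, where flooring is likelier. Neither step handles a zero or counts the records lost from the ratio.
- **Stakes.** The study is exploratory, without a hypothesis, and 2 of 14 variables of interest are affected.

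The objection does not remove the core: following the stated floor-then-log sequence selects records on their own outcome.

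**Conclusion.** The concern holds as a gap in the analysis rules for AUC0-5min and, to a lesser degree, AUC0-10min. The mechanism follows from the SAP text alone. How often it bites does not: LLOQ, assay error, baseline level and early rise are all absent, and under assumed values the effect goes from negligible to large.

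A reader might also infer a fixed direction, namely that dropping zeros always raises the low/high ratio. It does not. Small positive values that remain, including residuals from two samples below quantification, pull a product's geometric mean down, and some scenarios ended below the true ratio.

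No defect is shown for Cmax, Tmax or the later AUCs, and the sample size is unaffected. Nor do the documents give grounds for discarding the planned ratios: they are the estimand's summary measure, and zeros may not occur.

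**What to change.** 1. Keep the geometric mean ratios for all AUCs, and state in SAP 6.5.1 that zero AUCs are excluded from them.
2. Tabulate, by product and time point, the floored concentrations and the zero and near-zero AUC0-5min and AUC0-10min values. Define near-zero in advance, for example as an AUC built only from LLOQ/2 substitutions.
3. Pre-specify one further analysis of these two endpoints that keeps every profile: AUCs from unfloored corrected concentrations, compared on the original scale. Use either paired Hodges-Lehmann differences with 95% CI, as already planned for Tmax, or the same mixed model untransformed.
4. For any comparison in which zeros or residuals from values below quantification occur, base conclusions on early delivery on that analysis.

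The cost is SAP wording and one extra analysis of two exploratory endpoints, reported as differences beside ratios. Unfloored AUCs can be negative. The Hodges-Lehmann version is not adjusted for period and uses complete pairs only; the untransformed model keeps the adjustment. Data collection does not change.

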6.4 Pharmacokinetic Data Summarization and Presentation

SAS software (Version 9.4, Cary, North Carolina) will be used for all data presentation and summarization including statistical analyses, summary tables, graphs, and data listings.

Plasma nicotine concentrations (observed and background-corrected), λ_z (observed only), and other PK parameters (background-corrected only) will be summarized with descriptive statistics including number of subjects (n), number and percent of subjects with missing data (Missing, n (%)), arithmetic mean (Mean), standard deviation (SD), percent CV (CV%), standard error of the mean (SEM), minimum, first quartile (Q1), median, third quartile (Q3), and maximum.

Statistical Analysis Plan Number CA36095

In addition, geometric mean (Geo. Mean), 95% geometric confidence interval (Geo. 95% CI), and geometric CV (Geo. CV%) will be presented, as applicable.

For observed plasma nicotine concentrations, the number and percent of values below LLOQ (BLQ, n(%)) and above ULOQ (ALQ, n(%)) will be presented in each summary table.

Categorical variables will be summarized by frequency statistics (number and percentage).

For endpoints relating to sampling times (e.g., T_{max}) only n, missing n (%), median, Q1, Q3, minimum and maximum will be presented.

All analyses and summaries will be performed by product and overall. Summaries will be further stratified by sex.

The analytical data will be presented in the tables/listings to the same precision as received from the analytical laboratory.

The level of precision and rounding for the summary statistics will be specified in the TFL shell document.

Where individual data points are missing because of dropouts or other reasons, the data will be summarized based on reduced denominators. Missing PK data will be treated as missing, and no data imputation will be conducted.

Mean and individual plasma nicotine concentrations will be presented graphically (linear and semi-log plots; linear plots will be presented with and without SD).

6.5 Statistical Analysis of PK Parameters

6.5.1 Main analysis

A mixed model analysis of variance (ANOVA) will be conducted on AUC and C_{max} endpoints in the natural logarithmic scale.

The model will include terms for sequence, period, and product as fixed effects, and subject as a categorical random effect, modeling the within subject correlations.

A heterogeneous Compound Symmetry matrix will be used to model the variance covariance structure within subjects. If this model fails to converge, then the following variance-covariance matrices will be used (in this order) until one converges: variance Components, Compound Symmetry, and finally without subject's random effect.

The procedure will use the restricted maximum likelihood method and the Kenward-Roger method to compute the degrees of freedom.

The results of this analysis will be presented in terms of geometric least square mean ratios and 95% CI for the 4 respective variants of NP 1.0, Velo-NP, and Zyn-NP ratios. The pairwise comparisons which will be performed are listed in Table 6.2.

Philip Morris Products S.A.

Nicotine pouch (NP) 1.0, P5-PK-01-EXP

Statistical Analysis Plan Number CA36095

Table 6.2 List of pairwise comparisons

	NP-2	NP-3	NP-4	Velo-NP	Zyn-NP
NP-1	X	X	X	X	X
NP-2		X	x	X	X
NP-3			X	X	X
NP-4				X	X

The model described above will be implemented in the SAS® language as:

PROC MIXED data=dataset method=reml;

class Subject Sequence Period Product Sex;

model Log(Parameter) = Sequence Period Product / ddfm=KR;

repeated Product / subject=Subject type=csh;

lsmeans Product / pdiff=LIST OF PAIRWISE COMPARISONS cl;

RUN;

The analysis of T_{max} will be performed by conducting a Wilcoxon signed rank test and calculating the median T_{max} for each product along with the Hodges-Lehmann estimate of the median difference between products, and the related 95% CI.

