12.9.5 Determination of Sample Size and Power Consideration

The sample size is empirically based as there are no considerations for statistical hypothesis.

A total of 24 subjects is expected to be sufficient to obtain a precision of 15% or less on the NP-1: Velo-NP C_{max} ratio.

The precision has been determined using the following geometric coefficient of variation (GCV) and within subjects correlation assumptions for C_{max} :

- For all products the GCV of C_{max} is assumed to be 40%. [1]
- The correlation within subjects on log-transformed data is assumed to be 0.7. It has been derived as the correlation that would explain the width of the confidence interval of the C_{max} difference between the Zyn and Velo-NP product, as compared to the confidence interval of the C_{max} of Zyn-NP and Velo-NP product as described in [16].

The precision has been determined using 10,000 simulations performed with SAS®.

Confidentiality Statement

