Another ANCOVA will be conducted similarly to the above with the exception that it will be performed overall using mixed effects ANCOVA where the model will include, in addition, the subject as a categorical random effect to model the within subject correlations.

The ANCOVA analysis will be performed using the following SAS code:

PROC MIXED data=< > method=type3; By product sex; class subject sequence period; model log(PK parameter) = sequence period score/ddfm=KR solution; random subject; run;

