9. SUMMARY OF CHANGES FROM PROTOCOL-PLANNED ANALYSIS

In section 7.2 AUCs related to T1 to T11 for VAS craving assessment, VAS liking assessment and VAS satisfaction assessment have been added to the descriptive statistics.

In section 8.12, it is specified that the investigator will define ranges to determine normal or abnormal Spirometry results.

All other analyses described in this SAP are aligned with those analyses described in the protocol.

Statistical Analysis Plan Number CA36095

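### If the main model's CSH structure fails to converge, the stated fallback order can discard the crossover pairing, depending on how subject is coded

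*SAP*

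**What the plan says.** SAP 6.5.1 and Protocol 12.6.2.1 fit the same model to log Cmax and log AUCs, with sequence, period and product as fixed effects, REML, and Kenward-Roger degrees of freedom. The SAP text brings subject in as "subject as a categorical random effect, modeling the within subject correlations", and the protocol likewise as "subject as a categorical random effect modeling the within subject correlations".

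The code printed in both documents to implement that model has no RANDOM statement. Subject appears only in "repeated Product / subject=Subject type=csh".

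Only this CSH step is printed as code. The fallbacks are prose:

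- SAP 6.5.1: structures are tried "until one converges: variance Components, Compound Symmetry, and finally without" the subject random effect.
- Protocol 12.6.2.1: "Variance Components, Compound Symmetry, and finally no repeated statement".

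The two ladders end differently. SAP section 9 does not list this, and says "All other analyses described in this SAP are aligned with those analyses described in the protocol". Elsewhere, in the overall PK/PD ANCOVA of SAP 7.3, the code does contain a random-effect line: "random subject; run".

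Protocol 12.9.5 gives the planning expectation: "A total of 24 subjects is expected to be sufficient to obtain a precision of 15% or less on the NP-1: Velo-NP" Cmax ratio. It assumes a GCV of 40% and a within-subject log-scale correlation of 0.7, and does not define precision further.

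**The concern.** Because the fallbacks are not coded, two programmers could fit different models from the same text.

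- **Reading 1: the ladder changes TYPE= on the printed REPEATED statement.** The protocol's last step, which removes REPEATED, points this way. With no RANDOM statement, Variance Components on REPEATED is a single-variance, independent-errors model. It practically always converges, so Compound Symmetry, the natural simplification of CSH, is never tried. The protocol's last step would then give the same independence model again.
- **Reading 2: a RANDOM Subject term is fitted as well.** The SAP's last step, which removes the subject random effect, points this way. Subject plus independent residuals is then the same model as Compound Symmetry for non-negative correlation, and the Variance Components step loses nothing.

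At stake under reading 1 are the 14 pairwise ratio intervals (5 + 4 + 3 + 2 in the comparison table) of any endpoint whose CSH fit fails. They would ignore the pairing while other endpoints keep it. Protocol 12.9.4 names the point estimate and 95% CI as the form its inference takes, so interval width matters even without hypothesis tests.

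**Working it through.** **Inputs.** From Protocol 12.9.5: n = 24, GCV 40%, correlation ρ = 0.7; from the synopsis: true ratio 1. From SAP 3.1: six product-use periods and six sequences in a Williams design. My assumptions: four subjects per sequence, complete data, equal variances across products, and precision read as the upper 95% CI limit relative to a ratio of 1.

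Log-scale variance: σ² = ln(1 + 0.4²) = ln(1.16), so σ = 0.3853.

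**Step 1. The plan's own figure.** With pairing kept, SE = σ√(2(1 − ρ)/24) = 0.3853 × √(0.6/24) = 0.0609. Residual df with subjects absorbed: 144 − 24 − 5 − 5 = 110. Half-width = t(110) × SE = 0.1207, which is +12.8% / −11.4%. A normal quantile gives +12.7% and a paired t(23) gives +13.4%. All are below 15%, so the stated figure reproduces.

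**Step 2. Variance Components on REPEATED, no RANDOM statement.** Residual df: 144 − 1 − 5 − 5 − 5 = 128, of which 18 (24 − 6) are between subjects within sequence. The expected residual variance is

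E = σ²[18(1 + 5ρ) + 110(1 − ρ)]/128 = σ²(81 + 33)/128 = 0.891σ².

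Half-width = t(128) × √(2E/24) = 0.2077, which is +23.1% / −18.8%. Ratio to step 1: 0.2077/0.1207 = 1.72.

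**Step 3. Simulation.** In 10,000 simulated trials of this design the mean log half-widths were 0.1203 (Compound Symmetry) and 0.2055 (Variance Components). Coverage was 94.8% and 99.8%. The upper half-width was below 15% in 99.1% and 0.06% of trials. With complete balanced data the ratio estimates are the same under both models.

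**Step 4. Against the model actually abandoned.** In 60 simulated REML fits of CSH, the standard-error ratio of Variance Components to CSH had mean 1.69 and median 1.63. The interval ratio is therefore about 1.6 to 1.7, depending on degrees of freedom.

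**Step 5. Other correlations.** The protocol states 0.7 for Cmax only, so for the AUCs this range is an assumption. Log half-widths, with the upper side in brackets:

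| ρ | Pairing kept | VC on REPEATED | Ratio |
|---|---|---|---|
| 0.3 | 0.1844 (+20.2%) | 0.2148 (+24.0%) | 1.17 |
| 0.5 | 0.1558 (+16.9%) | 0.2113 (+23.5%) | 1.36 |
| 0.6 | 0.1394 (+15.0%) | 0.2095 (+23.3%) | 1.50 |
| 0.7 | 0.1207 (+12.8%) | 0.2077 (+23.1%) | 1.72 |
| 0.8 | 0.0986 (+10.4%) | 0.2058 (+22.9%) | 2.09 |

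**Step 6. Reading 2.** In five simulated trials fitted by REML, the standard error of a product difference agreed to five decimals between random subject with independent residuals and Compound Symmetry on REPEATED. In the first trial both were 0.05696, against 0.08517 for Variance Components on REPEATED alone.

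**Step 7. How often the trigger occurs.** CSH fits with a general optimiser, not PROC MIXED, converged in 120 of 120 simulated trials. The failure rate in SAS on real data is unknown.

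**The case against.** The harm needs two things together: CSH must fail, and reading 1 must be chosen. Failure looks uncommon, and within the SAP the prose leans to reading 2. It calls subject a random effect, its last step makes sense only if that effect is still present at the steps before, and SAP 7.3 shows the same authors coding such an effect. Protocol 12.1 makes the SAP the place for full statistical detail. This stands, and it is why the conclusion is conditional. It does not settle the matter, because the main-model code in that same SAP has no RANDOM statement and the protocol's last step speaks of REPEATED.

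Two further limits stand. The 1.72 compares with homogeneous Compound Symmetry rather than CSH, and no figure comes from datasets in which CSH actually failed. Precision is also undefined in the protocol. The correlation at which 24 subjects just meet 15% with pairing is 0.60 on the upper side, 0.46 on the lower side and 0.54 for a log half-width of 0.15, so any such threshold is an assumption. At ρ = 0.7, Variance Components misses 15% on all three.

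A reader might infer that the planned main model ignores the within-subject correlation because RANDOM is absent. It does not: CSH on REPEATED with Subject as the subject factor models that correlation, which is the role the text gives to subject. The mismatch matters only in the uncoded fallbacks.

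**Conclusion.** The point holds in conditional form and is minor. If CSH fails for an endpoint and the ladder is applied to the printed REPEATED statement, its ratio intervals lose the pairing. For Cmax under the protocol's assumptions that means about +23% instead of about +13%, roughly 1.6 to 1.7 times wider on the log scale, with coverage of about 99.8%. If subject is fitted through RANDOM, the Variance Components step costs nothing.

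A reader might also infer that the study would fail its precision requirement or report falsely precise ratios. The documents support neither. The 15% is a planning expectation in an exploratory study without a tested hypothesis, and the affected ratio intervals err towards being too wide. Tmax is analysed by other methods and is untouched.

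The statement that estimates do not move rests on complete balanced data. Protocol 12.6.2 sets some data to missing and relies on REML under MAR, where the covariance model can affect the estimates. The documents give no expected rate of missing data, so I put no size on that.

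The differing last steps are a documentation gap, since that step is unlikely to be reached.

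**What to change.** Edit SAP 6.5.1:

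- After CSH, go directly to Compound Symmetry and print it as code: `repeated Product / subject=Subject type=cs;`, or equivalently (for non-negative correlation) `random Subject;` with independent residuals. One of the two is enough; the second is not a further fallback to the first.
- Delete Variance Components on REPEATED, and delete the last step that drops the subject effect or the REPEATED statement.
- State whether subject enters through REPEATED or RANDOM, and make the text and code agree.
- Add one line to SAP section 9 recording that the fallback ladder differs from Protocol 12.6.2.1.

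The cost is a few words and one or two code lines in the SAP. Protocol 12.1 provides for changes to the statistical methods to be documented in the SAP and CSR, so no protocol amendment is needed. Design, data collection and sample size are unchanged.
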